#### 4.6.1. Required Adverse Event Reporting

Adverse event reporting will be consistent with BMT CTN procedures (BMT CTN Administrative Manual of Procedures, Chapter 6). It is BMT CTN policy that AEs must be reported even if the investigator is unsure whether a relationship exists between the adverse event and the use of study treatment. Unexpected, serious adverse events (SAEs) will be reported through an expedited AE reporting system via AdvantageEDC. Unexpected, lifethreatening and fatal SAEs must be reported within 24 hours of knowledge of the event. All other unexpected SAEs must be reported within three business days of knowledge of the event. Events entered in AdvantageEDC will be reported using NCI's Common Terminology Criteria for Adverse Events (CTCAE) Version 4.0. Expected AEs will be reported using NCI's Common Terminology Criteria for Adverse Events (CTCAE) Version 4.0 at regular intervals as defined on the Form Submission Schedule. Any expected life-threatening SAE not collected on another study form must be reported through the expedited AE reporting system via AdvantageEDC.

The Data and Safety Monitoring Board will receive summary reports of all unexpected SAEs on a semi-annual basis.

# CHAPTER 5

### 5. STATISTICAL CORRELATIONS

#### 5.1. Study Design

The study is designed as a Phase II randomized, open label, multicenter trial to identify whether sirolimus is a potential alternative to prednisone as an up-front treatment for patients with standard risk acute GVHD (defined by both refined Minnesota standard clinical risk and AA1/2 biomarker risk group). The hypothesis is that sirolimus will produce comparable response rates while also reducing steroid burden in this population. As this is the first trial prospectively assessing sirolimus in a multicenter setting, the trial is not designed to formally declare non-inferiority but rather to estimate the difference in response rates between the sirolimus arm and the prednisone (or standard of care) arm. Estimation of this difference along with establishing more precise estimates for a key secondary endpoint with a response definition incorporating a measure of steroid burden (requirement a patient is on less than 0.25 mg/kg at Day 28) will allow assessment of sirolimus as a potential upfront treatment for GVHD response.

Patients will be randomized to either sirolimus or prednisone. The primary endpoint is complete or partial response (relative to their GVHD status on the day of randomization) on Day 28 post-randomization with secondary endpoints assessing alternate definitions of efficacy, safety, steroid burden and quality of life. The target enrollment is 120 eligible, randomized AA1/2 patients. One hundred and fifty patients are expected to be randomized as approximately 20% of randomized patients will have AA3 status results or missing biomarker results and be removed from the primary analysis (see the Primary Endpoint Section for details).

#### 5.1.1. Accrual

It is estimated that accrual will take 2 years.

### 5.1.2. Randomization

Randomization will be performed in a 1:1 ratio using random block sizes for the two arms and stratified by transplant center.

#### 5.1.3. Primary Endpoint

The primary endpoint of the study is defined in Chapter 3. Briefly, the primary endpoint is complete or partial response of acute GVHD (as compared to status at day of randomization) on Day 28 post-randomization. Note that patients classified as AA3 per the biomarker criteria and patients with missing biomarker results will be excluded from the primary analysis (i.e. primary and secondary endpoints) population and described in a secondary analysis.

### 5.1.4. Primary Hypothesis

The primary hypothesis is that up front treatment with sirolimus will result in comparable CR/PR rates as up front treatment with prednisone. No formal hypothesis testing will take place. Instead

the difference in response rates between the two arms will be estimated with a 90% confidence interval.

#### 5.1.5. Sample Size and Power Considerations

The primary endpoint is CR/PR at Day 28 post-randomization. Background data on treatment with sirolimus is available for 27 standard risk (Minnesota Criteria) patients. The overall CR/PR rate in the population was 88.9% (95% CI 77.0%, 100.0%). If patients receiving any level of prednisone are considered failures (per Chapter 3) then the observed CR/PR rate was 55.6% (95% CI 36.8%-74.3%). Considering background data from BMT CTN 0802, data were available for 95 placebo treated patients meeting the standard risk criteria at GVHD onset. The response rate in that population was 64.2% (95% CI 54.6%-73.9%). Note that PR was not formally adjudicated by the Endpoint Review Committee for BMT CTN 0802. Instead a response of Better Grade (compared to grade at diagnosis) was adjudicated and considered here as a surrogate for PR. While the point estimates differ slightly, the confidence intervals for the two populations are overlapping. Table 5.1 shows the lower bound of a 90% asymptotic confidence interval given two scenarios: 1) success rate of 60% in each arm and 2) success rate of 60% in the prednisone arm and 50% in the sirolimus arm (sirolimus response rate is 10% lower).

Table 5.1: Lower Bound of Asymptotic 90% Confidence Interval For Difference in Response Rates Between Sirolimus and Prednisone Arms Assuming Equal Rates (60%) and a 10% Lower Response Rate in the Sirolimus Arm With a 20% Inflation Due To Biomarker Results

Randomized	Analyzed	N Analyzed Per Arm	Lower Bound of 90% Confidence Interval Assuming No Difference Between Treatment Arms*	Lower Bound of 90% Confidence Interval Assuming Sirolimus Response Rate is 10% Lower*
125	100	50	-16%	-26%
150	120	60	-15%	-25%
175	140	70	-14%	-24%
200	160	80	-13%	-23%
225	180	90	-12%	-22%
250	200	100	-12%	-22%

\* Difference calculated as Sirolimus response rate minus Prednisone response rate.

The number randomized assumes that 20% of randomized patients will have biomarker results indicating high risk disease (AA3) or missing biomarker results. Note that 60 analyzable patients per arm (150 randomized) will result in a lower bound of 15% assuming that the success rates in the two populations are equivalent. If sirolimus is 10% worse than the prednisone arm, the lower bound of the confidence interval will exceed 15%. Difference in Day 28 CR/PR rate across the two arms will be reported with associated 90% confidence interval, however no pre-planned difference or width of confidence interval will be used to indicate failure of either arm or serve

as a requirement for consideration of secondary endpoints (i.e. formal non-inferiority will not be declared in this trial). A key secondary endpoint is the proportion of patients in CR/PR with a steroid dose of  $\leq 0.25$  mg/kg by Day 28. Of the 95 placebo patients, 22.1% (95% CI 13.8% - 30.5%) achieved a CR/PR by Day 28 and were receiving  $\leq 0.25$  mg/kg. This estimate may not be reliable, however, as the taper for BMT CTN 0802 suggested a minimum of 0.25 mg/kg on Day 28 as such this may be an underestimate of the true rate. Using the upper end of the confidence interval, sixty patients per arm would provide 80.6% power (two-sided 5% type 1 error rate) to test for a difference of 25% between the two groups (30% Prednisone vs. 55% Sirolimus).

# 5.2. Interim Analysis and Stopping Guidelines

# 5.2.1. Interim Analysis

There will be no interim analyses for efficacy or futility as this is a small phase II study.

# 5.2.2. Guidelines for Safety Monitoring

Monitoring of two key safety endpoints will be conducted monthly, and if rates significantly exceed pre-set thresholds, the NHLBI will be notified in order that the DSMB can be advised. Policies and composition of the DSMB are described in the BMT CTN's Manual of Procedures. The stopping guidelines serve as trigger for consultation with the DSMB for additional review. The key safety endpoints for this study are: 1) failure of sirolimus therapy with a failure for the stopping rule defined as the addition of a systemic immune suppressive therapy beyond prednisone among those patients originally treated with sirolimus and 2) overall mortality. Both of these endpoints will be monitored among AA1/2 patients only; failure of sirolimus therapy will be monitored in the sirolimus arm only.

### 5.2.2.1 Day 42 Failure of Sirolimus Therapy

The rate of sirolimus failure will be monitored up to 42 days post-randomization. At least three events must be observed in order to trigger review. The expected probability of 42 day sirolimus failure is approximately 25-30% (estimate derived from primary sirolimus monotherapy data, as well as anticipated rate of secondary therapy use beyond prednisone in prior BMT CTN aGVHD therapy trials). Each month, the null hypothesis that the 42-day sirolimus failure rate is less than or equal to 25% is tested. For this rule, a binomial sequential probability ratio test (SPRT) will be implemented.

This sequential testing procedure conserves type I error at 5% across all of the monthly examinations for the sirolimus arm. The SPRT can be represented graphically. At each monthly interim analysis, the number of evaluable patients on study is plotted against the total number of treatment failures. The continuation region of the SPRT is defined by two parallel lines. Only the upper boundary will be used for monitoring to protect against excessive 42-day sirolimus failure. If the graph crosses the upper boundary, the SPRT rejects the null hypothesis, and concludes that there are more events than predicted by the number of evaluable patients on study. Otherwise, the SPRT continues until enrollment is complete. Only failures that occur on or before the patient has been followed for 42 days are counted.

The boundaries for the binary SPRT were constructed by setting the null rate of sirolimus failure to be 25% versus an alternative of 50% for 42-day sirolimus failure. To construct the boundary, the nominal type I and type II errors were set to be 10% and 5% respectively. The upper boundary is defined by a slope of 0.36907 and an upper intercept of 2.04921. Since the upper boundary alone is being used, the actual type I error of the binomial SPRT will be less than the nominal value without a substantial increase in type II error for the alternatives of interest (i.e. sirolimus therapy failure rates higher than expected). Table 5.2.1 illustrates the number of observed events required to cross the boundary for the binomial SPRT.

Number Evaluable Patients	Number of Events On or Prior to Day 42
4-5	4
6-7	5
8-10	6
11-13	7
14-16	8
17-18	9
19-21	10
22-24	11
25-26	12
27-29	13
30-32	14
33-35	15
36-37	16
38-40	17
41-43	18
44-45	19
46-48	20
49-51	21
52-54	22
55-56	23
57-59	24
60	25

 TABLE 5.2.1: Safety Monitoring Guidelines for Failure of Sirolimus Therapy

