#### 2.5.7. Management of study therapy after GVHD Progression or Non-response:

The following guidelines describe intended management of initial randomized therapy and thresholds for starting secondary therapy:

1. Initial randomized therapy should be given for at least 4 days before considering initiation of secondary therapy. As progressive manifestations of GVHD (new organ involvement or increased organ specific symptoms sufficient to increase the organ stage by one or more) can be ultimately stabilized and controlled in this initial therapy timeframe, secondary therapy should only be considered if GVHD continues to progress after this period.

2. If no response (no improvement in any affected organ) is observed after 7-10 days of initial randomized therapy, secondary therapy can be considered.

# CHAPTER 3

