# 5.2.2.2 Day 56 Overall Mortality

Day 56 overall mortality is the second key safety endpoint. This endpoint will be monitored within each treatment arm using an extension of the (SPRT) for censored exponential data, as described in greater detail below and in Appendix D. In brief, unlike the binary SPRT which assesses the event rate in the number of evaluable patients, the censored exponential SPRT considers the number of events relative to the total at risk time observed on study. The SPRT is represented graphically with the number of events on the y-axis and the total at risk time on the x-axis. The upper boundary of the SPRT will be used to guard against excess mortality. This procedure assumes a censored exponential distribution for overall mortality during the first 56 days, and censors follow-up time after 56 days.

Based on background data for standard risk acute GVHD patients, the expected Day 56 overall mortality is 13.1%. As this estimate includes AA3 patients in addition to AA1/2, to be conservative, the null for the monitoring bound will be set at 10%. An SPRT contrasting 10% vs 25% Day 56 overall mortality results in decision boundaries with a common slope of 1.18 and an upper intercept of 2.29 based on nominal type 1 and type II errors of 9% and 10% respectively with the type I and II errors selected based on the simulation study and the actual operating characteristics of the SPRT shown in Table 5.2.2 that assumed uniform accrual of 60 individuals over a 24 month time period, and exponential time to failure after randomization.

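### The Day 42 sirolimus-failure rule is said to hold type I error at 5%, but the published boundary gives about 3.4%, 5.8% or 8.6% at the planned accrual, depending on a counting rule the plan does not state

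*Protocol*

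**What the plan says.** Protocol 5.2.2.1 tests, each month, a null 42-day failure rate of 25% or less against an alternative of 50% in AA1/2 patients on sirolimus, using the upper boundary of a binomial SPRT. The overall error claim is: "This sequential testing procedure conserves type I error at 5% across all of the monthly examinations for the sirolimus arm". SAP 2.5 makes the same claim.

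The boundary uses nominal errors of 10% (type I) and 5% (type II). The only support for a lower figure is that, with the upper boundary alone, "the actual type I error of the binomial SPRT will be less than the nominal value".

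On counting, the plan says that at each look "the number of evaluable patients on study is plotted against the total number of treatment failures", and adds: "Only failures that occur on or before the patient has been followed for 42 days are counted". On duration: "Otherwise, the SPRT continues until enrollment is complete".

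For the mortality rule, by contrast, Protocol Table 5.2.2 and SAP Table 2.3 report simulated operating characteristics and name the accrual assumption.

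**The concern.** A bound of *below the nominal 10%* does not establish 5%, and nothing else in either document supports the 5%. Appendix D's worked example, also built with a nominal type I error of 10%, simulates at 7%. It is a different design, so it shows only that a nominal 10% does not by itself give 5%.

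The actual error also depends on a term left open. *Evaluable* is both the plotted quantity and the row heading of Table 5.2.1. The one counting sentence limits which failures qualify. It does not say whether a Day 10 failure counts before that patient reaches Day 42, or whether patients still short of Day 42 are in the denominator. Two statisticians could apply Table 5.2.1 to the same data and disagree on whether the boundary has been crossed.

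The DSMB uses the stated error to judge how surprising a crossing is. Protocol 5.2.2.1 itself expects a failure rate of about 25–30%, so the behaviour of the rule at 30% matters too, and it is not reported.

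**Working it through.** **Inputs from the documents.** Null rate p0 = 0.25, alternative p1 = 0.50, nominal α = 0.10 and β = 0.05 (Protocol 5.2.2.1); 60 analyzable patients per arm (Protocol 5.1.5); monthly looks. The mortality simulation "assumed uniform accrual of 60 individuals over a 24 month time period"; I apply the same accrual here, which is 60/24 = 2.5 sirolimus patients a month.

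**Assumed.** The documents give no distribution for the day of failure. I take it as uniform on days 4 to 42. The lower limit comes from Protocol 2.5.7: "Initial randomized therapy should be given for at least 4 days before considering initiation of secondary therapy".

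**Step 1: the boundary reproduces.**
- Denominator: ln[p1(1−p0)/(p0(1−p1))] = ln[0.375/0.125] = ln 3.
- Slope: ln[(1−p0)/(1−p1)]/ln 3 = ln 1.5/ln 3 = 0.36907.
- Intercept: ln[(1−β)/α]/ln 3 = ln 9.5/ln 3 = 2.04921.
- Events needed at n patients: slope × n + intercept, rounded up. At n = 60: 22.144 + 2.049 = 24.19, so 25. Every row of Table 5.2.1 matches.

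**Step 2: exact error on the printed table.** Binomial recursion at 25%, truncated at 60 patients with complete outcomes, gives 7.5% with a look after every patient, 6.3% every 2 patients, 5.35% every 3 and 5.6% every 5. At 2.5 patients a month, with the cumulative count rounded down, it gives 6.2%. None is 5% or less.

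**Step 3: monthly looks in calendar time.** Simulation with 300,000 replicates and looks ending at month 24. Entries are the percentage of trials that cross.

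| Counting rule | 25% | 30% | 40% | 50% |
|---|---|---|---|---|
| Only patients with 42 days completed | 5.8 | 17 | 65 | 96 |
| Failures as they occur (denominator: failed or 42 days completed) | 8.6 | 22 | 71 | 97 |
| All enrolled in the denominator | 3.4 | 12 | 58 | 95 |

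Running the looks on to month 27 leaves the 25% column at 5.8, 8.6 and 3.4.

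**Step 4: sensitivity of the 25% column** (200,000 replicates, Monte Carlo standard error about 0.06 points).

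| Varied | 42 days completed | As they occur | All enrolled |
|---|---|---|---|
| Failure days, from 35–42 to 4–14 | unaffected | 6.3 to 11.4 | 2.4 to 4.7 |
| Accrual over 12 months | 4.7 | 10.3 | 1.5 |
| Accrual over 18 months | 5.3 | 9.0 | 2.6 |
| Accrual over 36 months | 6.2 | 8.1 | 4.4 |

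With exponential or uniform failure times over the whole 42 days, and random or evenly spaced entry, the three readings give 5.3–5.8%, 8.1–9.1% and 3.5–3.7%. A mixed count, setting all failures to date against only those patients with 42 days completed, gives about 11–15%, above even the nominal 10%. The text does not exclude it.

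**Step 5: size of the excess.** 5.8 − 5 = 0.8 points, and 1/0.008 = 125, so about 1 trial in 125. 8.6 − 5 = 3.6 points, and 1/0.036 ≈ 28, so about 1 in 28.

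**The case against.** The strongest reply is that nothing has been shown to be miscalculated. With all enrolled patients in the denominator, the error stays below 5% in every sensitivity above (1.5–4.7%), and the plan does not rule that reading out. With 42 days completed, the excess is under one point. It disappears if accrual takes 12 months, and the plan rounds its own figures (0.053 for mortality becomes 5%). The 8.6% rests on assumed failure timing. Failure here means adding an agent beyond prednisone, which may come after prednisone has been tried, so days 4 to 14 is an extreme case. Finally, "The stopping guidelines serve as trigger for consultation with the DSMB for additional review", so nothing stops automatically.

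Much of this stands. The figures are conditional, and later failures do lower the as-they-occur figure: 7.6% for days 14–42 and 7.1% for days 21–42. But that is still above 5%, as is the most favourable timing tried (6.3%). The all-enrolled reading fits poorly with the word *evaluable* for a 42-day binary outcome. Faster accrual brings the error under 5% only on the completed reading; it raises it when failures count as they occur. The claim of 5% is made without any of these conditions.

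**Conclusion.** The concern holds, and it is minor. The 5% is unsupported. At 24-month accrual it is not met on either reading in which patients count once their 42-day status is known: 5.8% with 42 days completed and 8.6% with failures counted as they occur. It is met, at 3.4%, only if all enrolled patients are in the denominator. These values rest on uniform accrual of 60 patients and on failure days spread over 4 to 42. Power against 50% is about 95–97% on all three readings, so excess failure would not be missed. The cost is a misstated design property, some additional alerts and an ambiguous count.

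**What to change.** In Protocol 5.2.2.1 and SAP 2.5:

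1. Add a sentence saying which patients are in the denominator and when a failure counts.
2. Replace 5% with the computed figure for that counting rule.
3. Add an operating-characteristics table at true rates of 25, 30, 40 and 50%, with the accrual and failure-timing assumptions stated, as Table 5.2.2 does for mortality. The matching row of the Step 3 table can be used if its assumptions are accepted; otherwise rerun it under the team's own.

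The cost is one sentence and one corrected figure in each document, plus one small table. The boundary, Table 5.2.1, data collection and trial conduct do not change.

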# 5.2.2.2 Day 56 Overall Mortality

Day 56 overall mortality is the second key safety endpoint. This endpoint will be monitored within each treatment arm using an extension of the (SPRT) for censored exponential data, as described in greater detail below and in Appendix D. In brief, unlike the binary SPRT which assesses the event rate in the number of evaluable patients, the censored exponential SPRT considers the number of events relative to the total at risk time observed on study. The SPRT is represented graphically with the number of events on the y-axis and the total at risk time on the x-axis. The upper boundary of the SPRT will be used to guard against excess mortality. This procedure assumes a censored exponential distribution for overall mortality during the first 56 days, and censors follow-up time after 56 days.

Based on background data for standard risk acute GVHD patients, the expected Day 56 overall mortality is 13.1%. As this estimate includes AA3 patients in addition to AA1/2, to be conservative, the null for the monitoring bound will be set at 10%. An SPRT contrasting 10% vs 25% Day 56 overall mortality results in decision boundaries with a common slope of 1.18 and an upper intercept of 2.29 based on nominal type 1 and type II errors of 9% and 10% respectively with the type I and II errors selected based on the simulation study and the actual operating characteristics of the SPRT shown in Table 5.2.2 that assumed uniform accrual of 60 individuals over a 24 month time period, and exponential time to failure after randomization.

# TABLE 5.2.2: OPERATING CHARACTERISTICS OF SEQUENTIAL TESTINGPROCEDURE FROM A SIMULATION STUDY WITH 10,000 REPLICATIONS

True 56-Day Rate	10%	15%	20%	25%
Probability Reject Null	0.053	0.281	0.641	0.888
Mean Month Stopped	25.2	22.1	16.8	12.0
Mean # Endpoints in 56 Days	5.8	7.6	7.9	7.0
Mean # Patients Enrolled	58.2	51.6	40.4	29.6

**Day 56 Overall Mortality** 

If the true Day 56 overall mortality rate is in line with the expected rate (i.e. 10%), then the stopping guideline has a 5% probability of being triggered. If the true overall mortality rate is higher than expected (i.e. 25% by Day 56), then the stopping guideline has an 89% probability of being triggered (on average 12 months after opening when 30 patients have been enrolled).

No monitoring of secondary therapy delivered beyond prednisone will be performed in the prednisone arm, as this treatment is considered standard of care. We will prospectively monitor the rate of AA3 participants which is expected to be 20% of standard risk patients. This rate will be reported (with a 95% confidence interval) to the DSMB at each semiannual meeting to determine if the rate is higher than expected.

### 5.2.3. Demographic and Baseline Characteristics

Demographics and baseline characteristics will be summarized for all patients. Characteristics to be examined are: age, gender, race/ethnicity, performance status, primary disease, risk status, transplant conditioning therapy characteristics, donor type and HLA mismatch, graft source,

initial GVHD prophylaxis delivered, donor and recipient CMV status, acute GVHD organ staging and overall grade at enrollment, topical steroid therapy use. Between group comparisons will be performed for continuous variables via a t-test (or Wilcoxon Rank-Sum) and for categorical variables, via the chi-square test (or Fisher's Exact as appropriate).

